9.4.2 Outcome Definitions

Malignancy: Any occurrence of malignant neoplasms during the study period. These will be grouped and classified by type. Malignancies will include all pathologically confirmed solid tumors (excluding non-melanoma skin cancer) and hematological malignancies, as the primary outcome for all malignancies-related analyses. Benign tumors will not be collected. The pre-defined groups are the following:

- Any malignancies excluding non-melanoma skin cancer (NMSC) (primary)
- Any malignancies including NMSC
- Solid tumors only
- Hematological tumors only

Severe infections:

The following categories will be investigated:

- Tuberculosis
- PML
- Opportunistic infections (excluding herpetic infections, tuberculosis, and PML): defined as an invasive infection caused by microorganisms that are normally non-pathogenic or rarely pathogenic in individuals with normal immune function or cause an infection of a type or severity not seen in the normal host.
- Other severe infections

All bacterial, viral, fungal, parasitic and protozoal infections that occur during the study period and regardless of the duration of infection will be recorded. The duration of infections will be the difference between start date and recovery date as reported by the treating physician. Patients may contribute for more than one episode to this analysis if, after resolution as defined, another infection occurs.

An infection will be considered severe if it leads to a significant impairment of functioning, i.e., the subject is unable to carry out usual activities. This definition includes serious and non-serious infections, in line with the definition used in the RMP of oral cladribine. An infection is considered serious if it fulfills at least one of the following seriousness criteria: results in death, is life-threatening, requires in-patient hospitalization or prolongation of existing hospitalization, results in persistent or significant disability/incapacity, is a congenital anomaly/birth defect, or is otherwise considered as medically important.

As the availability of data related to certain infections may vary among the databases, detailed operational definitions for the identification of severe and opportunistic infections in different disease coding systems used by data sources of the study will be defined in the statistical analysis plan (SAP).

Herpes zoster infections: Regardless of the severity.

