Norwegian Patient Registry	100% of the population with inpatient or special outpatient care visits in Norw
Cancer Registry of Norway	100% of the population with cancer in Norway
Cause of Death Registry	100% of the deceased population in Norway
SWEDEN	
MS registers	
Swedish MS Registry	Approximately 80% (14,500 patients) of the Swedish MS patients (Hillert et a 2015)
National healthcare registers	
Swedish Prescribed Drug Register	100% of the population with prescribed drugs purchased in community pharmacies in Sweden
National Patient Register	100% of the population with inpatient or special outpatient care visits in Sweden
Swedish Cancer Register	100% of the population with cancer in Sweden
Cause of Death Register	100% of the deceased population in Sweden
MULTI-COUNTRY	
MSBase ^{a,b}	Approximately: 48 sites, 24 972 MS patients Australia: 20 sites, 4,314 patients Belgium: 4 sites, 877 MS patients Czech Republic: 2 sites, 3,499 MS patients The Netherlands: 3 sites, 839 MS patients Spain: 8 sites, 2,471 MS patients Switzerland: 2 sites, 491 MS patients Italy: 10 sites, 4,606 MS patients Italy: 6 sites, 2,764 MS patients UK: 3 sites, 505 MS patients

^a Number of MS patients with at least 1 visit between January 1, 2014 and December 31, 2016.

Each of the data sources listed in Table 1 is further described in Appendix 2.

In the Nordic countries, every resident has a Personal Identity Number (PID). All the registers listed in Table 1 include the PID, enabling linkage of the data across all registers and thus capture of the needed data for the study. The data linkage is described in further detail in Section 9.7.1.

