9.8.2 Derived and Transformed Data

Calculation of person-years of follow-up

Follow-up time for each patient will be calculated from the cohort entry date (initiation of oral cladribine or fingolimod) to the earliest of the following: event of interest, death, end of follow-up, withdrawal of informed consent, emigration or loss to follow-up. For a given non-recurrent event (e.g. first malignancy), the patient follow-up will not be censored for the other events of interest, and the patient will continue to contribute to the risk time for these other events.

Severe lymphopenia duration

Severe lymphopenia duration is defined as the interval from the finding of severe lymphopenia (Grade \geq 3) until the finding of its resolution (Grade 1 or 0). Given that no regular blood tests are requested per protocol, there is a risk to overestimate the duration of lymphopenia. However, in patients with severe lymphopenia, this risk of bias will be reduced because the physician would be expected to perform a closer follow-up with more frequent blood testing.

Handling of missing data

Methods commonly used in non-interventional studies for handling missing data will be applied. Descriptive analyses will be performed using available data. The number of patients with missing data will be reported for each measured variable in the study. In descriptive analyses, missing data will be described separately and not included in the denominator for the calculation of the percentage for each category of a particular variable.

Full details on handling missing data will be described in more detail in the SAP which will describe the methods for identifying where missing data methods should be applied, the techniques for identifying the type of missing information and the appropriate imputation methods to be used, if any, as per European Medicines Agency (EMA) 2011 guidance on missing data.

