9.8.3 Statistical Methods

Descriptive analyses

For continuous variables, the following measures will be reported: the number of patients with non-missing data, the number of patients with missing data, mean, standard deviation, median, quartiles, and minimum and maximum. For categorical variables, the number of non-missing observations (number and percentage of total non-missing; n, % of total), as well as the number of patients with missing data will be reported.

Description of analysis sets and characteristics at enrolment

Number and percentage of patients per cohort (cladribine or fingolimod) will be presented by analysis sets as well as by participant country.

The description of demographic characteristics and other characteristics at enrolment for both cohorts will be presented using summary tables to allow a general comparison. Appropriate statistical tests will be applied to compare the cohorts. Further details on methodology will be provided in the SAP.

Assessment and comparison of safety outcomes

Primary analysis

Using the intention-to-treat exposure definition, the crude and adjusted incidence rates of the different AESIs along with 95% CIs will be estimated in both oral cladribine patients and fingolimod patients. The following categories of AESI will be considered: malignancies (excluding NMSC), herpes zoster infections, tuberculosis, PML, other opportunistic infections, and other severe infections.

To compare the incidence of AESI between oral cladribine patients and fingolimod patients adjusting for key prognostic factors (as defined *a priori* in the SAP for each AESI), the incidence rates ratios of the AESI together with the 95% CIs will be estimated by Poisson regression models

adjusted for the key prognostic factors (including prior use of immunomodulatory/immunosuppressive agents) and displayed by means of forest plots.

Sensitivity analyses for the primary analysis

The following sensitivity analyses will be performed for the primary analysis:

- 1) For the analyses regarding malignancies, 2 sensitivity analyses excluding all malignancies occurring within 6 and 12 months after cohort entry will be performed to account for the latency period for malignancies to develop (induction period of 6 and 12 months after treatment initiation).

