The Swedish National Patient Register, managed by the National Board of Health and Welfare, covers virtually 100% of the Swedish population (10 million in 2017). This register has data since 1987. It covers all inpatient care since 1987 and special outpatient care from 2001 onwards. Primary care data is not included in this register. Recorded variables include eg, discharge diagnoses (ICD-9 or -10 codes) and performed medical procedures. Currently the National Patient Register is updated monthly. Access to the register data for scientific research is applied from the National Board of Health and Welfare through a standard application procedure.

Swedish Cancer Registry

Swedish Cancer Registry has data since 1958. It contains information on eg, date of diagnosis and details of the tumor (site, histological type and stage), but not on treatment. Data for the year before previous year are available in January (eg, data for 2016 are available in January 2018).

Cause of Death Register

The Cause of Death register has data since 1953. The information recorded includes eg, cause of death (ICD-10 codes have been used since 1998), time of death, and intention in cases of injury or poisoning. The reporting rate is virtually 100%. Data for previous year are available in August. Access to the register data for scientific research is applied from the National Board of Health and Welfare through a standard application procedure.

Norway

Each permanent resident (staying at least for 6 months) in Norway has a unique PID that carries information on the date of birth and gender. All the data sources listed below include information on PIDs that enables linkage of data from different sources.

Norwegian MS Registry and Biobank

The Norwegian MS Registry and Biobank has been established in 2001. On national level, approximately 55% of the Norwegian MS patients are included in the register. The register includes detailed data on the MS patients, with data on eg, characteristics of the disease as well as the treatment and laboratory measurements (including lymphocyte counts). Access to the register data for scientific research is applied directly from the register through a standard application procedure.

Norwegian Prescription Database

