Norwegian Prescription Database is managed by the Norwegian Institute of Public Health and it contains data since 2004. This national register covers virtually 100% of the Norwegian population (5.2 million in 2017). The data cover all prescribed drugs dispensed at pharmacies. Drugs used in hospitals and institutions are not recorded in this register. The Norwegian Prescription Database contains information on eg, date of purchase, trade name, ATC code, strength, and package size of the drug. Data for previous year are available in April. Access to the register data for scientific research is applied from the Norwegian Institute of Public Health through a standard application procedure.

Norwegian Patient Registry

Norwegian Patient Registry is managed by the Norwegian Directorate of Health. This national register has data since 2008 and it covers virtually 100% of the Norwegian population (5.2 million in 2017). It contains information on patients who have been referred to hospital treatment but are still on a waiting list for treatment, or who have been treated at hospital, medical outpatients' clinic or at contract specialist clinic. The data cover hospitalization details such as diagnoses (ICD-10 codes) and medical procedures. Lag time in data availability is approximately 3 to 6 months. Access to the data for scientific research is applied from the Norwegian Directorate of Health through a standard application procedure.

Cancer Registry of Norway

Cancer Registry of Norway is managed by Oslo University Hospital Trust, and it contains data since 1951. Recorded data consist of eg, tumor characteristics (site, topography, morphology, metastatic status, stage) as well as of medical procedures performed and type of treatment given. Data for previous year are available in December. Access to the register data for scientific research is applied from the register holder through a standard application procedure.

Cause of Death Registry

The Cause of Death Registry is managed by the Norwegian Institute of Public Health, and it has data since 1951. The main variables recorded in this register are cause of death (ICD-10 codes) and time of death. The reporting rate virtually 100%. Data for previous year are available in November. Access to the register data for scientific research is applied from the Norwegian Institute of Public Health through a standard application procedure.

Denmark

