In this national register, data are updated twice a year. Data from January to June are usually available in August the same year, and data from July to December in February the following year. Access to the registry data for scientific research is applied from the Danish Health Data Authority through a standard application procedure. The Applicant must be a Danish public research organization. It is not allowed to transfer individual-level data from the server of the Danish Health Data Authority. This means that all analyses using data from this registry (with or without linked data from other data sources) must be conducted at the server of this authority.

National Patient Register

National Patient Register, managed by the Danish Health Data Authority, covers virtually 100% of the Danish population (5.7 million in 2017) admitted to somatic hospitals, emergency rooms, and specialty outpatient clinics (secondary care) in Denmark. This register has data on admissions to hospitals since 1977, and on admissions to emergency rooms and outpatient clinics since 1995. Data from primary care and psychiatric care are not included in the National Patient Register.

The National Patient Register contains information on hospitalization details such as type of treatment, and diagnoses and operations in secondary care. Data for the previous year are usually available in March. Access to the register data for scientific research is applied from the Danish Health Data Authority through a standard application procedure. The Applicant must be a Danish public research organization.

Danish Cancer Registry

Danish Cancer Registry has data since 1943 including all incident malignant neoplasms (and certain precancerous and benign lesions) with information on eg, date of diagnosis and tumor characteristics (morphology, topography, behavior, stage). Data for the year before previous year are available in January (eg, data for 2016 are available in January 2018).

Danish Register of Causes of Death

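### Zoster of any severity and non-serious severe infections use all person-time as denominator, including sources that do not see primary care, so pooled absolute rates for these two outcomes are biased low

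*Protocol*

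**What the plan says.** **Outcomes.** Protocol 9.4.2 states "Herpes zoster infections: Regardless of the severity". Severe infection is defined by loss of usual functioning, and "This definition includes serious and non-serious infections, in line with the definition used in the RMP of oral cladribine".

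**Measure and denominator.** In the primary analysis (9.8.3), "the crude and adjusted incidence rates of the different AESIs along with 95% CIs will be estimated" in each cohort. In 9.8.2, "Follow-up time for each patient will be calculated from the cohort entry date" to the event or censoring. Nothing restricts it by data source or by what a source can record.

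**Sources.** Appendix 2 says of the Swedish patient register: "Primary care data is not included in this register". Of Denmark it says: "Data from primary care and psychiatric care are not included in the National Patient Register". For Norway, Table 1 (9.5.1) gives "100% of the population with inpatient or special outpatient care visits in Norw" (cut off in the text read), and Appendix 2 says "It contains information on patients who have been referred to hospital treatment" or were treated at hospitals, outpatient clinics or contract specialists. Only Finland lists a primary-care register and an infectious-disease register. For OFSEP, the Italian registry and MSBase, Table 1 shows no linked health registers.

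**Capture.** Section 9.5.1 says that linkage by personal identity number brings in the data the study needs. Section 9.10 accepts that routine data may be incomplete, but it does not name infections treated in primary care.

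**The concern.** Both outcomes include events that need not lead to a hospital or specialist contact. A patient whose zoster is treated only in primary care in Sweden, Denmark or Norway adds person-time to the rate. The episode enters the numerator only if it reaches an MS register. The rate then falls because events were not seen, and its confidence interval carries sampling error only.

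Absolute rates are half of the primary objective, which is to characterise the risk as well as compare it. Zoster is also the infection for which Section 7 reports an excess in the trials: 0.86 against 0.20 adjusted events per 100 person-years for cladribine 3.5 mg/kg and placebo.

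**Working it through.** The protocol gives no figure for ascertainment, so there is none to reproduce. The check has three parts.

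**1. Do other routes close the gap?**
- Sweden: IMSE supplements the MS registry, but Appendix 2 describes it as recording the more important adverse events.
- Denmark: the treatment register holds follow-up on side effects while patients are on medication. Its safety module is still in preparation.
- Norway: the MS registry is described as holding disease, treatment and laboratory data.
- All secondary-use sources: 9.2.5 says that only what the physician judged relevant is recorded. The mandatory outcomes listed there do not name zoster.
- Prescription registers: 9.4.1 uses them for exposure and concomitant medication, not to find outcomes.

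These routes reduce the shortfall. As described, they do not remove it.

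**2. Size for the absolute rate.** Let λ be the true rate, T the person-years, s the share of T in the affected sources and u the share of their events that reach no study source. Assume the same λ everywhere and full capture elsewhere. Recorded events are λT(1 − s) + λTs(1 − u) = λT(1 − su), so observed/true = 1 − su.

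The documents give neither s nor u. The assumed ranges, for Sweden, Denmark and Norway together, are s = 10% to 45% and u = 30% to 90%. Applied to 0.86 per 100 person-years:

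| s | u | su | rate seen |
|---|---|---|---|
| 10% | 30% | 3% | 0.83 |
| 20% | 50% | 10% | 0.77 |
| 20% | 70% | 14% | 0.74 |
| 30% | 70% | 21% | 0.68 |
| 40% | 90% | 36% | 0.55 |
| 45% | 90% | 40.5% | 0.51 |

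Within the affected sources alone the rate is low by u itself. If OFSEP, the Italian registry and MSBase also miss events, their own s × u terms add to the shortfall.

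For event counts, the 32,907 person-years at Year 15 in Tables 3 and 4 are per cohort. With 0.26 per 100 person-years and a true ratio of 1, SE = √(2/(32,907 × 0.0026)) = 0.153. The probability of excluding 1.5 is then Φ(ln 1.5/0.153 − 1.96) = 75.6%, against 74% in Table 4. Read as a two-cohort total, it would be 46.6%. So 0.86 per 100 person-years gives 283 events. At s = 20%, u = 70% this becomes 243, a rate of 0.74 with 95% CI 0.74 × exp(±1.96/√243) = 0.65 to 0.84, which misses the true 0.86. This count assumes zoster is recorded over all follow-up; the relative shortfall does not need that assumption.

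**3. Effect on the rate ratio.** With equal s and u in both cohorts, 1 − su cancels and the ratio is unbiased. Its SE grows by 1/√(1 − su): 1.5% at (10%, 30%) and 25% at (40%, 90%). If source mix differs and the model ignores source, take u = 70%, s = 40% for cladribine and 20% for fingolimod. A true ratio of 1 is then seen as (1 − 0.28)/(1 − 0.14) = 0.84; with the mix reversed, 1.19.

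**The case against.** **Left to the SAP.** Section 9.4.2 admits that infection data vary between databases and leaves operational definitions to the SAP. Variable definitions are to follow in Appendix 1, and nothing bars reporting by source. This stands in part. However, the deferral names severe and opportunistic infections, not zoster. Code lists also cannot recover visits that no register receives, and the denominator rule is fixed in 9.8.2.

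**Capture may be better than feared.** The patient registers include specialist outpatient care, and the Danish one includes emergency rooms. Reporting to the Danish treatment register is compulsory, and variables can be added to it. Neurologist visits are about three-monthly in Denmark and Norway and six-monthly in Sweden (9.1.1). No document says what share of these infections is managed in primary care. All of this stands: it limits the size, not the direction. For Norway, the absence of primary care is inferred from the register's described scope.

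**Stronger readings the documents do not support.**
- *All AESI rates are too low.* Each Nordic country has a cancer register with full coverage. The argument does not reach tuberculosis, PML, opportunistic or serious infections diagnosed in hospital or specialist care. Finland is largely unaffected.
- *The comparison with fingolimod is biased.* That needs differential capture or source mix. Danish side-effect data tied to medication, with short cladribine courses against daily fingolimod, could cause it. So could the closer observation of cladribine patients foreseen in 9.10. Neither the net direction nor the size can be stated.
- *The interval is falsely precise.* On the log scale its width depends on the event count, so missed events widen it. The fault is that it is centred too low.
- *The result will be set against the trial rate.* No such comparison is planned; 0.86 serves here only as an illustration.

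**Conclusion.** The point holds for herpes zoster of any severity and for non-serious severe infections. As written, their pooled absolute rates are biased low unless the MS registers catch every such infection treated only in primary care, and nothing in the protocol supports that. For these two outcomes the capture statement in 9.5.1 does not agree with Appendix 2 for Sweden and Denmark or, by its described scope, for Norway.

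The shortfall is s × u. The range of about 3% to 40% rests on assumed values of both inputs and is not an estimate; the documents allow no single corrected rate. The rate ratio is safe under equal capture and equal source mix, and at risk otherwise. The defect should be corrected in the plan, but it does not undermine the study's main comparison or its malignancy analysis.

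**What to change.** - **9.8.2 and 9.8.3:** make person-time outcome-specific for these two outcomes. Report their absolute rates by data source or ascertainment type. Label the Swedish, Danish and Norwegian rate as hospital- or specialist-treated or MS-register-reported, and do not present the pooled figure as an any-severity rate.
- **OFSEP, Italian registry, MSBase:** apply the same by-source reporting, since they have no linked health registers.
- **NTD and MSDS 3D:** do not treat these as complete, because entries come from the neurologist or study staff. Section 11.4 records AESI other than malignancy for 4 years, so end their denominator there.
- **Finland:** state that the primary-care register covers publicly organised care only.
- **Rate ratio:** stratify or adjust by data source.
- **Antiviral dispensing:** use it only as a supporting sensitivity definition of zoster. Indication is optional free text in the Swedish and Danish drug registers, so it would exchange missed events for misclassified ones.
- **9.10 and 9.5.1:** name the gap in the first and correct the capture statement in the second.

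The cost is revised wording and a source flag in the analysis data; the Nordic registers are already to be linked. Each reported rate will rest on fewer person-years and have a wider interval.
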